11.2. Clinical Laboratory Evaluations

Clinical laboratory test results in SI units will be summarized descriptively and will include a display of change from baseline to each post-dose scheduled time point. Baseline values for all lab tests will be the last non-missing value on or before date of first treatment.

Laboratory values outside of the normal ranges will be identified. Clinically significant hematologic and non-hematologic laboratory abnormalities that meet Grade 3 or Grade 4 criteria according to the CTCAE will be listed and summarized. Clinical laboratory values will be presented using the reported units.

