 - d. Incidental histologic finding of prostate cancer (T1a or T1b using the tumor, nodes, metastasis [TNM] clinical staging system)
11. Significant active cardiac disease within the previous 6 months, including:
- a. New York Heart Association (NYHA) class IV congestive heart failure (see [Appendix G](#));
 - b. Unstable angina or angina requiring surgical or medical intervention; and/or
 - c. Myocardial infarction
12. Uncontrolled systemic fungal, bacterial, or viral infection (defined as ongoing signs/symptoms related to the infection without improvement despite appropriate antibiotics, antiviral therapy, and/or other treatment)
13. Known Human Immunodeficiency Virus (HIV) or Hepatitis C (HCV) infection, or evidence of active Hepatitis B Virus (HBV) infection
14. Any of the following laboratory abnormalities:
- a. Serum AST/SGOT or ALT/SGPT > 2.5 x ULN
 - b. Serum total bilirubin > 1.5 x ULN. Higher levels are acceptable if these can be attributed to active red blood cell precursor destruction within the bone marrow (ie, ineffective erythropoiesis). Subjects are excluded if there is evidence of autoimmune hemolytic anemia manifested as a corrected reticulocyte count of > 2% with either a positive Coombs' test or over 50% of indirect bilirubin
 - c. Serum creatinine > 2.5 x ULN
 - d. Absolute WBC count $\geq 20 \times 10^9/L$
15. Known or suspected hypersensitivity to azacitidine, mannitol, or durvalumab, its constituents, or to any other humanized monoclonal antibody
16. Pregnant, planning to become pregnant starting from 28 days prior to receiving CC-486 or durvalumab, throughout your participation in the study, and for at least 90 days following your last dose of study treatment, or breast-feeding females
17. Any significant medical condition, laboratory abnormality, or psychiatric illness that would prevent the subject from participating in the study
18. Any condition including the presence of laboratory abnormalities, which places the subject at unacceptable risk if he/she were to participate in the study
19. Any condition that confounds the ability to interpret data from the study, including known or suspected conditions other than MDS, associated with anemia
20. Having received any prior MAb against CTLA-4, PD-1, or PD-L1 or having received other investigational MAbs within 6 months
21. Clinical evidence of central nervous system (CNS) or pulmonary leukostasis, or CNS leukemia

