For subjects entering the study with pre-existing Neutropenia Grade 4, treatment should be started at the regular starting dose and schedule of 200 mg BID 21/28d. However, if neutropenia continues to worsen under treatment, dose modification may be considered as summarized in Table 4.

For any subject who experiences a worsening of neutropenia to Grade 4 for ≥ 4 days, independent of whether considered related to IP or not, a dose modification may be considered as summarized in [Table 4](#).

Dose Modification for Diarrhea

It is recommended that subjects experiencing diarrhea be managed according to the guidelines provided in [Appendix H](#). Anti-diarrhea medication may be administered as prophylaxis against diarrhea and for treatment of any adverse events of diarrhea. Recommended dose modification steps for diarrhea (\geq Grade 2) are summarized in [Table 4](#). If further dose-reduction beyond modification Step -3 (or the QD *rescue* regimen) is thought to be necessary, IP should be discontinued and the treatment discontinuation visit scheduled.

Dose Modification for Nausea and Vomiting

A serotonin (5-HT₃) receptor antagonist (eg, ondansetron) or other comparable medication may be administered as an antiemetic prophylaxis approximately 30 minutes prior to IP administration if necessary. Antiemetic pretreatment is recommended during the first cycle of the treatment phase. If the subject does not experience significant nausea and/or vomiting, further use of antiemetic medications may not be necessary. Antiemetic medication(s) should be administered for treatment of any adverse events of nausea and/or vomiting. Recommended dose modifications for nausea and vomiting (\geq Grade 3) are summarized in [Table 4](#). If further dose-reduction beyond modification Step -3 (or the QD *rescue* regimen) is thought to be necessary, IP should be discontinued and the treatment discontinuation visit scheduled.

Dose Modification for Renal Dysfunction and Abnormal Serum Electrolytes

If unexplained elevations of serum creatinine or electrolyte disturbances occur, dose or schedule modifications may be implemented as summarized in [Table 4](#). If further dose-reduction beyond modification Step -3 (or the QD *rescue* regimen) is thought to be necessary, IP should be discontinued and the treatment discontinuation visit scheduled.

Dose Modification for Weight Change

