
Neutropenia Grade 4 (related or unrelated to IP)
	
Pre-existing Neutropenia Grade 4
 
 • Continue IP at the discretion of the investigator 
 – If the neutropenia continues to worsen significantly under treatment in the investigator’s opinion, treatment may be temporarily interrupted. – Resume IP after the ANC has improved or stabilized (as assessed by the investigator). IP dose/schedule may be reduced at the investigator’s discretion (see Table 3). • If the subject continues to experience Grade 4 neutropenia during 2 consecutive cycles, IP dose/regimen should be reduced by at least 1 step (Table 3). Secondary prophylaxis with G-CSF may be considered. 
Subjects experiencing worsening of Neutropenia to Grade 4 during IP treatment
 
 • Continue IP at the discretion of the investigator 
 – If episode persists for ≥ 4 days, IP may be temporarily interrupted. – Resume IP after the ANC has improved or stabilized (as assessed by the investigator). IP dose/schedule may be reduced at the investigator’s discretion (see Table 3). • If the subject continues to experience Grade 4 neutropenia during 2 consecutive cycles, IP dose/regimen should be reduced by at least 1 step (Table 3). Secondary prophylaxis with G-CSF may be considered.

Diarrhea (≥ Grade 2)
	
 • Interrupt IP and provide adequate/maximum medical intervention • Resume IP at same dose when toxicity resolves to ≤ Grade 1 • If event reoccurs upon re-challenge or during the subsequent treatment cycle, modify IP dose/schedule by at least 1 step according to Table 3.

**Table 4: Guidelines for CC-486 Toxicity Management and Dose Modifications
 (Continued)**

NCI CTCAE Toxicity Grade	Action
Nausea and/or Vomiting (≥ Grade 3)	
 • Interrupt IP and provide adequate/maximal medical intervention • Resume IP at same dose when toxicity resolves to ≤ Grade 1 • If event reoccurs upon re-challenge or during the subsequent treatment cycle, modify IP dose/schedule by at least 1 step according to Table 3.

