11.4. ECOG Performance Status

ECOG performance will be summarized categorically with a shift from baseline by cycle, end of study and maximum shift by treatment. Individual subject data will be listed. The last ECOG performance score prior to and including the date of the first dose of study drug will be used as the baseline value.

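### The Grade 3-4 laboratory summary takes no account of baseline grade, so it can count unchanged pre-existing cytopenia alongside on-treatment worsening

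*SAP*

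**What the plan says.** The rule for graded laboratory results is one sentence, identical in SAP 11.2 and protocol 10.7: "Clinically significant hematologic and non-hematologic laboratory abnormalities that meet Grade 3 or Grade 4 criteria according to the CTCAE will be listed and summarized". Two conditions select a result: it reaches Grade 3 or 4, and it is clinically significant, a term the SAP does not define.

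Baseline enters SAP 11.2 in two other places. The descriptive summaries of laboratory values "will include a display of change from baseline to each post-dose scheduled time point", and baseline itself is defined: "Baseline values for all lab tests will be the last non-missing value on or before date of first treatment". Neither is tied to the Grade 3-4 summary.

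Elsewhere the SAP does plan a categorical shift, but for performance status only (SAP 11.4): "ECOG performance will be summarized categorically with a shift from baseline by cycle".

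On the population, protocol 8.2.4.1 provides for severe cytopenia at entry: "For subjects entering the study with pre-existing Neutropenia Grade 4, treatment should be started" at the regular dose and schedule. Table 4 in the same section treats these patients separately from a second group: "Subjects experiencing worsening of Neutropenia to Grade 4 during IP treatment". Exclusion criterion 14 (protocol 7.3) limits liver enzymes, bilirubin and creatinine. Its only haematologic limit is an upper one, on "Absolute WBC count".

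**The concern.** In MDS a low count is often the disease itself. A summary that selects results by the grade reached, without asking what the grade was before the first dose, mixes two kinds of patient: those already at Grade 3-4 who stayed there, and those who moved to Grade 3-4 on treatment. Only the second group says anything about tolerability.

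Two features of the trial make the mixture harder to see through. The combination arm was stopped (SAP 13), so the monotherapy results have no concurrent comparator in which baseline cytopenia would show up. In addition, SAP 11 presents safety by disease cohort, and inclusion criterion 4 lets a patient qualify as progressive disease through sustained falls in granulocytes, platelets or haemoglobin. Baseline cytopenia may therefore differ between the SD and PD cohorts by definition, and a difference between them in a raw Grade 3-4 count could reflect entry status and not the drug.

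At stake is how readable this laboratory table is as evidence on the first secondary objective, safety and tolerability.

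**Working it through.** The plan gives no figure for this table, so there is nothing to reproduce. The check is mainly a comparison of texts, followed by an illustration.

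**1. Does the rule exclude unchanged baseline cytopenia?** Take a patient with Grade 4 neutropenia before and throughout treatment. The grade condition is met. No worsening condition exists to remove the patient, and no post-dose window is stated. Only the clinical-significance condition could do so, and it is undefined. Protocol 8.2.4.1 uses Grade 4 neutropenia as its example of an event that may put a subject at unacceptable risk even when unrelated to treatment, so such a result could well be called significant.

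**2. Can such a patient be enrolled?** Yes, explicitly for neutropenia (protocol 8.2.4.1 and Table 4). For platelets and haemoglobin it follows from the absence of a lower limit in criterion 14. Appendix F also defines a platelet response for patients starting below 20 x 10⁹/L.

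**3. Does another planned output supply the missing step for laboratory grades?**
- Change from baseline (SAP 11.2) works on values at scheduled visits. It does not show how many patients moved into Grade 3-4.
- The planned shift (SAP 11.4) covers ECOG only.
- The adverse event rule (SAP 11.1) does require onset or worsening after the first dose, but it applies to reported adverse events. Under protocol 11.3 a laboratory value becomes an adverse event only if it leads to discontinuation or intervention, or is judged clinically important.

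So no laboratory-grade comparison with baseline is planned.

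**4. Illustration of size.** Inputs: n = 16, the Stage 1 cohort size (SAP 4.3). Let b be the proportion at Grade 3-4 at baseline and i the proportion of the remaining patients who newly reach Grade 3-4. Neither is in the documents; I assume b from 10% to 75% and i from 10% to 50%. I also assume that every patient at baseline Grade 3-4 stays at that grade and that the clinical-significance condition removes none of them.

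- Shown in the table: b + (1 − b) × i
- On-treatment worsening, as a share of all patients: (1 − b) × i
- Pre-existing share of the count: b / [b + (1 − b) × i]

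For b = 25% and i = 30%: 0.25 + 0.75 × 0.30 = 0.475, or 7.6 of 16. Worsened: 0.75 × 0.30 = 0.225, or 3.6 of 16. Pre-existing share: 0.25 / 0.475 = 53%.

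| b | i | Shown (of 16) | Worsened (of 16) | Pre-existing share |
|---|---|---|---|---|
| 10% | 50% | 55.0% (8.8) | 45.0% (7.2) | 18% |
| 25% | 30% | 47.5% (7.6) | 22.5% (3.6) | 53% |
| 50% | 30% | 65.0% (10.4) | 15.0% (2.4) | 77% |
| 75% | 10% | 77.5% (12.4) | 2.5% (0.4) | 97% |

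The first and last rows are the extremes of the assumed range. A span from 18% to 97% shows that the mixture may be minor or may dominate, and that the documents cannot say which.

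**The case against.** The strongest reply is that haematologic toxicity is not judged from this table. The safety endpoint (protocol 3.2, SAP 4.2.2) is framed in terms of adverse events: their type, frequency, severity and relationship to study drug. The treatment-emergent tables in SAP 11.1 count an event only if it begins or worsens after treatment starts. Myelosuppression is a listed category there, with its own tables for Grade 3 or 4, serious events, withdrawal, dose reduction and interruption. That stands, and it limits the point considerably.

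A reader might infer that the laboratory table is the one on which toxicity is judged, and hence that the safety objective is defeated or myelosuppression overstated. The documents do not support this. No section gives the laboratory table that role, and the adverse event tables already separate stable cytopenia from worsening.

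It can also be said that the clinical-significance condition may screen out some unchanged cytopenia, and that the table shells, which are not among the documents, might add a baseline column. Both are possible, but neither is written down. The finding is about what the text permits, not about what a final table will show.

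What the reply does not remove is that the adverse event tables depend on investigators' reporting judgement, while the laboratory data are the objective check on them. With different baseline rules, the two sources can disagree for that reason alone.

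**Conclusion.** As written, SAP 11.2 and protocol 10.7 let unchanged pre-existing cytopenia be counted together with on-treatment worsening, in a population that may enter at Grade 4 neutropenia with no floor on ANC, platelets or haemoglobin. This weakens one descriptive supporting table. It does not defeat the safety objective, and it leaves the primary endpoint and the two-stage design untouched.

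Its size is unknown. The percentages above rest on assumed baseline prevalence and incidence, on baseline grades staying put, and on the clinical-significance condition removing nobody. They show direction and possible range only; a reader should not take any of them as an estimate of how far this trial's table is inflated. The point is a cheap improvement worth making.

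**What to change.** Keep the Grade 3-4 summary, which protocol 10.7 requires, and add the following to SAP 11.2.

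- **Shift tables**, by cohort, from baseline CTCAE grade to worst post-baseline grade, for ANC, platelets, haemoglobin, WBC and graded chemistry.
- **Window:** the one SAP 11.1 uses for treatment-emergent events, which ends 28 days after the last CC-486 dose and 90 days after the last durvalumab dose.
- **Treatment-emergent Grade 3-4:** a post-baseline grade of 3 or 4 that is higher than the baseline grade. The denominator is subjects below Grade 4 at baseline.
- **Baseline Grade 3 and Grade 4** in separate rows. A subject at Grade 4 cannot move to a higher laboratory grade, so describe further falls in these subjects with the change from baseline already planned.

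A sentence saying what makes an abnormality clinically significant would also help.

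The cost is one extra table per parameter. Baseline is already defined for every laboratory test, and hematology and chemistry go to the central laboratory on a fixed schedule (protocol 6.7.7). Because that section also allows some local results into the case report form, the SAP should say whether they count towards the worst grade.

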11.3. Vital Sign Measurements

Vital sign measurements reported in CRF and physical examinations will be summarized descriptively, and listed for each subject at baseline and each visit after, and change from baseline will be summarized. A listing of vital signs will be provided.

11.4. ECOG Performance Status

ECOG performance will be summarized categorically with a shift from baseline by cycle, end of study and maximum shift by treatment. Individual subject data will be listed. The last ECOG performance score prior to and including the date of the first dose of study drug will be used as the baseline value.

11.5. Bone Marrow Aspirate, Biopsy, and Peripheral Blood Smear

Bone marrow and peripheral blood samples will be collected at screening and following every 2 cycles of treatment during the first 6 treatment cycles (i.e., Cycle Day 28 [\pm 14 days]). Subjects who continue beyond Cycle 6 will undergo bone marrow examination following every 3 treatment cycles or when necessary to confirm suspected hematologic response or disease progression, and again upon treatment discontinuation. The data collected in CRF will be summarized in table and listing.

11.6. Electrocardiogram

An electrocardiogram (ECG) will be conducted and analyzed locally at screening and at treatment discontinuation by the local laboratory. The ECG is to be performed using the internationally recognized 12-leads. The investigator will review the results and assess as normal, abnormal - not clinically significant, or abnormal - clinically significant, and will report abnormal finding(s) on the respective CRF. If the ECG is abnormal, the investigator should consult a cardiologist if deemed appropriate. The ECG data from CRF will be summarized.

12. INTERIM ANALYSIS

An Independent Data Monitoring Committee will review the safety data during the safety run-in phase. The committee will also review the efficacy and safety data during the randomized phase of the study, in addition to the recommendation for any cohort to continue to stage-2 of the study. The details of the data monitoring plan will be provided in a separate charter document.

13. PHARMACOKINETIC ANALYSES

The following PK analyses were planned but not conducted in the combination arm which was stopped since the optimal combination dose could not be determined. Only a few subjects were enrolled in the combination arm who agreed to PK sample collection and due to the limited samples collected, the PK TLGs will not be generated.

13.1 CC-486

13.1.1 Plasma concentrations

By-subject listing of pharmacokinetic blood sample collection times as well as derived sampling time deviations will be provided. CC-486 plasma concentrations will be summarized using descriptive statistics (N, arithmetic mean, standard deviation, standard error, minimum, median, maximum, percent coefficient of variation, geometric mean, and geometric percent coefficient of variation).

Concentrations that are below the limit of quantitation (BLQ) will be treated as zero for the computation of descriptive statistics. Missing concentrations and concentrations from blood samples collected more than $\pm 10\%$ of nominal time will be omitted from the calculation of descriptive statistics.

Individual subject concentration-time data and mean concentration-time data for each cycle will be graphically presented on linear and semi-logarithmic scales.

Following dose administration, pre-dose samples that are BLQ or missing will be assigned a numerical value of zero for the calculation of AUC. Following the first administration, any anomalous concentration values observed at pre-dose will be identified in the study report and used for the computation of AUC. Pharmacokinetic parameters will be computed if the anomalous value is not greater than 5% of the C_{max} . If the anomalous value is greater than 5% of C_{max} , the computed PK parameters for the given subject will be dropped from the PK analysis.

Any other BLQ concentrations will be assigned a value of zero if they precede quantifiable samples in the initial portion of the profile. A BLQ value that occurs between quantifiable data points, especially prior to C_{max} , will be evaluated to determine if an assigned concentration of zero makes sense, or if reanalysis or exclusion of the data is warranted. Following C_{max} , BLQ values embedded between two quantifiable data points will be treated as missing when calculating AUC. Values below the quantifiable limit, occurring at the end of the collection interval (after the last quantifiable concentration), will be treated as missing data. If consecutive BLQ concentrations are followed by quantifiable concentrations in the terminal portion of the concentration curve, these quantified values will be excluded from the PK analysis by assigning them a value of missing, unless otherwise warranted by the concentration-time profile. For the purpose of analysis, these trailing BLQ values may be designated as zero in the dataset if the PK program used to do the analysis (such as WinNonlin[®]) will treat trailing zero values as missing when calculating AUC.

Actual sampling times will be used in the calculations of pharmacokinetic parameters that will be derived using non-compartmental (NCA) methods with Phoenix[™] WinNonlin[®] Professional

Version 6.4, or higher, (Pharsight®, a Certara™ company, St. Louis, Missouri). Graphics may be prepared with SAS Version 9.3, or higher; or Excel 2007, or higher; Phoenix™ WinNonlin® Professional 6.4, or higher.

13.1.2 PK Parameter

The following PK parameters will be calculated for CC-486:

- $AUC_{0-\infty}$ Area under the plasma concentration-time curve from Time 0 extrapolated to infinity, calculated as $[AUC_{0-t} + C_t/\lambda_z]$. C_t is the last quantifiable concentration. No AUC extrapolation will be performed with unreliable λ_z . If %AUC_{extrap} is $\geq 25\%$, $AUC_{0-\infty}$ will not be reported.
- AUC_{0-t} Area under the plasma concentration-time curve from Time 0 to the time of the last quantifiable concentration, calculated by linear trapezoidal method when concentrations are increasing and the logarithmic trapezoidal method when concentrations are decreasing.
- C_{max} Maximum observed plasma concentration, obtained directly from the observed concentration versus time data.
- T_{max} Time to C_{max} , obtained directly from the observed concentration versus time data.
- $t_{1/2}$ Terminal phase half-life in plasma, calculated as $[(\ln 2)/\lambda_z]$. $t_{1/2}$ will only be calculated when a reliable estimate for λ_z can be obtained.
- CL/F Apparent total clearance, calculated as $[Dose/ AUC_{0-\infty}]$.
- V_z/F Apparent volume of distribution, calculated as $[(CL/F)/\lambda_z]$.

The following PK parameters will be calculated for diagnostic purposes and listed, but they will not be summarized:

| | |
|------------------------|---|
| λ_z | Apparent terminal rate constant, calculated by linear regression of the terminal portion of the log-concentration versus time curve in plasma. Visual assessment will be used to identify the terminal linear phase of the concentration versus time profile. A minimum of three data points will be used for calculation. λ_z will not be estimated if the terminal phase of the log-concentration versus time profile does not exhibit a linear decline phase, or if the regression coefficient < 0.8 . |
| λ_z lower | Lower limit of time (h) included in the calculation of λ_z . |
| λ_z N | Number of data points used in the calculation of λ_z . |
| λ_z upper | Upper limit of time (h) included in the calculation of λ_z . |
| Rsq | Regression coefficient for calculation of λ_z . |
| %AUC _{extrap} | Percentage of AUC _{0-∞} due to extrapolation from the last quantifiable time point to infinity. |

